9. ASSESSMENT OF SAFETY AND EFFICACY

9.1 Assessment of Safety (Definition)

9.1.1 Adverse event:

Any untoward medical occurrence associated with the use of PRIM-DJ2727 whether or not considered drug related, and can therefore be

- Any symptom not previously reported by the subjects (medical history/pre-treatment diary). Wherever possible, a specific disease rather than individual associated signs and symptoms should be identified by the investigator. However, if an observed or reported sign or symptom is not considered a component of a specific disease by the investigator, it should be recorded as a separate adverse event.
- Clinical worsening of baseline parameters according to subject.
- A condition felt to be possibly related to treatment first detected or diagnosed after study drug administration

All adverse events (AEs) that occur within 180-200 days after treatment will be recorded as indicated above. Recurrence of CDI is not to be recorded as an adverse event unless hospitalization ≥ 24 hours is required for management, then recorded as serious adverse event.

9.1.2 Suspected adverse reaction:

Any adverse event for which there is a reasonable possibility that the study drug caused the adverse event. For the purposes of IND safety reporting, "reasonable possibility" means

there is evidence to suggest a causal relationship between the drug and the adverse event.

9.1.3 **Serious adverse event:**

Any adverse event or suspected adverse reaction is considered serious if in the view of the investigators it results in any of the following outcomes:

- Death
- Life-threatening adverse event
- Hospitalization \geq 24 hours
- Prolongation of existing hospitalization
- Substantial disruption of the ability to conduct normal life functions
- Congenital abnormally/birth defect
- Important medical events that jeopardize the patient, such as allergic bronchospasm requiring intensive treatment
- Persistent or significant incapacity or substantial disruption of the ability to conduct normal life functions

An emergency room visit without hospital admission will not be recorded as a serious adverse event (SAE) under this criterion, nor will hospitalization for a procedure scheduled or planned before signing of informed consent.

Death and life-threatening AEs possibly related to the study are reported by study coordinator or investigator within 24 hours to the IRB. Other SAEs potentially related to the study will be reported to the IRB within 7 days.

9.1.4 Unexpected adverse event:

An adverse event or suspected adverse reaction is considered 'unexpected' if it is not described in the general investigational plan or is not listed at the specificity or severity that has been observed.

9.1.5 Adverse events of special interest (weight gain, new or worsening autoimmune conditions, and metabolic syndrome):

Adverse events of special interest such as new or worsening autoimmune conditions and metabolic syndrome will be asked from subjects during follow up phone visits. Subjects will be asked at the enrollment visit that how much they weighed before the first CDI episode to take into consideration any weight loss resulting from CDI bouts. To obtain baseline data, subjects will be weighed on treatment day 1 clinic visit prior to administration of FMT treatment. After FMT treatment, subjects will be recommended to measure weight at home each Sunday morning before eating and record on follow up diaries, providing they have a scale or balance.

To account for normal weight fluctuations, subject-reported weekly weight data from diaries will be assessed for AE (>5% change from baseline weight) at days 60 and 180 phone visits.

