9.6 Recording and Documenting Adverse Event

The study team must completely and promptly record each new adverse event and serious adverse event that occurs after the procedure, even if the relationship of adverse event to the procedure is assessed by the Investigator to be “unlikely” or “not related”. In addition, the investigator must document and follow serious adverse events and adverse events of special interest that occur from the procedure through 180-200 days after the FMT. The Investigator should attempt, if possible, to establish a diagnosis based on the presenting signs and symptoms. If an adverse event meets the definition of a serious, unexpected and suspected (related to study drug/procedure) adverse reaction (SUSAR) then the Investigator must also complete the serious adverse event form/IND safety report, and send any supporting source documents to the University of

Texas Health Science Center IRB and FDA as soon as the event is discovered within the defined timeline.

At each visit, after the subject has had an opportunity to mention any problems spontaneously, the Investigator (or designee) will inquire about adverse event by asking the standard questions listed, such as:

- Have you had any new medical problems since your last visit?
- Have any medical problems present at your last visit changed, i.e., stopped, worsened, or improved?
- Have you taken any new medicines, other than study drug, since your last visit?

Any spontaneous adverse event information provided by the subject will be recorded. If an adverse event has not resolved at the time of the final visit, the Investigator should evaluate the status of the adverse event at the follow-up phone contact and reflect the status of the adverse event (e.g. ongoing or resolved).

The DSMB will issue a final report identifying adverse events related to study drug.

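### One item of the adverse event definition (9.1.1) makes possible relatedness a condition for counting a new diagnosis, so symptomless diagnoses judged unrelated may go unrecorded

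*Combined protocol and SAP*

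**What the plan says.** Section 9.1.1 opens without regard to cause: "Any untoward medical occurrence associated with the use of PRIM-DJ2727 whether or not considered drug related". Three items follow as forms such an event can take:

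- a symptom the subject had not reported before, with the instruction "Wherever possible, a specific disease rather than individual associated signs and symptoms should be identified by the investigator";
- worsening of baseline parameters, as the subject sees it;
- "A condition felt to be possibly related to treatment first detected or diagnosed after study drug administration".

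The section then ties recording to this list: "All adverse events (AEs) that occur within 180-200 days after treatment will be recorded as indicated above".

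Section 9.6 says the study team "must completely and promptly record each new adverse event and serious adverse event that occurs after the procedure, even if the relationship" is judged unlikely or absent. Section 9.3.2 gives four causality grades: probable, possible, unlikely and not related. Section 10.2.5 tabulates adverse events by relationship. Sections 2 and 9.11 make safety a primary endpoint, and 10.2.3 plans safety comparisons among groups 1 to 3 and between groups 3 and 4.

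**The concern.** Recording should come before attribution. If an investigator must first think a condition possibly related before it counts as an adverse event, the data hold only what that investigator already suspected. Nobody can later review the events that were set aside, because they were never written down.

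Here this touches a primary endpoint. After the treatment visit, follow-up is by phone, so a diagnosis made by the subject's own physician reaches the study as a reported condition. The third item is the one that names such a report. Group 4 is open, so the person making the judgment may know the subject's group. Staff who apply 9.1.1 literally and staff who apply 9.6 could build different safety data sets from the same reports.

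**Working it through.** The plan states no figure on this point, so the check is a comparison of text.

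**Step 1. Is there a contradiction inside 9.1.1?** The lead sentence, "Any untoward medical occurrence associated with the use of PRIM-DJ2727 whether or not considered drug related, and can therefore be", does not depend on cause. The first two items carry no causality condition, in keeping with it. The third does: a condition first found after dosing is listed only when someone thinks it possibly due to treatment. The item conflicts with the sentence that introduces it.

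**Step 2. Does it conflict with the rest of the plan?** Yes. A condition that enters through the third item alone has already been judged at least possibly related. When it is graded under 9.3.2, the two lower grades (unlikely, not related) are ruled out by the way it entered. Yet 9.6 expects events with those grades to be recorded, and 10.2.5 expects to tabulate by relationship. Both show that the plan means to hold unrelated events.

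**Step 3. Do other sections repair it?** Only in part.

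- 9.6 covers each new adverse event, but that term takes its meaning from 9.1.1. It does not clearly bring in something 9.1.1 has left out.
- 9.1.3 builds the serious adverse event on the same term, so the wording carries forward.
- The standard question in 9.6 about new medical problems draws out the information. It does not say which answers become adverse events.
- 9.7 tells an investigator who is unsure to record the finding. It does not cover one who is confident that the condition is unrelated.

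**Step 4. Which events are exposed?**

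| New condition after dosing | Route into the data | Causality condition? |
|---|---|---|
| With a new symptom | 9.1.1 first item (recorded as the disease where possible); 9.5 | No |
| With worsening of baseline | 9.1.1 second item; 9.5 | No |
| Autoimmune disease or metabolic syndrome | Asked about by name (7.2, 8.5, 9.1.5); documented and followed under 9.6 | None stated in those sections |
| No new or worsening symptom, thought at least possibly related | 9.1.1 third item | Yes, and met |
| No new or worsening symptom, thought unlikely or not related | Lead sentence of 9.1.1 and 9.6 only, against the third item | Yes, and not met |

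Only the last row is at risk. An incidental finding by the subject's physician is an example.

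**Step 5. How large is the loss?** It would need the rate of symptomless new diagnoses and the share judged unrelated. The documents give neither, so no count or percentage can be derived.

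**The case against.** The strongest reply is that the lead sentence governs and already includes events whatever their cause. The words that introduce the list can be read as offering examples, so the third item need not exclude anything. Bullet one, bullet two and 9.5 admit anything symptomatic or worsening. The question about new problems, the lowest grade in 9.3.2, the default in 9.7 and the tabulation in 10.2.5 all push staff towards recording. To lose an event, someone would have to follow one bullet against all of these.

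Much of this stands. It narrows the exposed group to the last row of the table and makes loss possible rather than certain. It does not remove the conflict. The third item is a stated rule, 9.1.1 says recording follows the list, and the helpful sections either borrow the term defined there or cover only an unsure investigator.

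Three stronger readings are tempting, and the documents do not support them.

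- *All newly diagnosed unrelated conditions are lost.* Symptomatic and worsening conditions enter without a causality test.
- *The special-interest events are filtered out.* "Adverse events of special interest such as new or worsening autoimmune conditions and metabolic syndrome will be asked from subjects during follow up phone visits" carries no relatedness condition, 9.6 separately requires these events to be documented and followed, and weight has its own trigger of more than 5% change from baseline.
- *The group 3 versus group 4 comparison is distorted, or power is lost, by a known amount.* The openness of group 4 makes unequal judgment possible, but the documents give no direction or size for it. Section 10.2.5 plans counts, percentages and listings of adverse events and names no test whose power could be computed. All four groups receive active product, and groups 3 and 4 the same dose, so their contrast could not show that the product causes a condition.

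**Conclusion.** The point holds in a limited form. The third item of 9.1.1 is wrong as written: it contradicts its own lead sentence, 9.6, 9.3.2 and 10.2.5. As a result, a diagnosis first made after dosing that brings no new or worsening symptom and is judged less than possibly related may go unrecorded.

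The size cannot be stated from the documents. The conclusion assumes that at least some staff apply the third item literally. If all follow the lead sentence and 9.6, nothing is lost. Severity is minor. It is still worth correcting, because the item puts a causality judgment ahead of recording on a primary safety endpoint in a partly open trial.

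**What to change.** Delete the phrase about being felt possibly related from the third item of 9.1.1, so that it covers any condition first found after dosing, whatever its suspected cause. Assign relationship afterwards, using the four grades in 9.3.2. The definition then agrees with 9.6 and with the tabulation in 10.2.5.

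The cost is one line of protocol text. No dose, visit or clinical rule changes. The small downside is that some more unrelated events will have to be recorded and coded.

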7. STUDY PROCEDURES

7.1 Duration of Participation

The duration of study participation is up to 216 days. It includes the enrollment period up to 14 days, 2 days of treatment, and 180-200 days of follow up for treatment effect and safety.

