7.3 Clinical Response Evaluation

The clinical evaluation will include an evaluation of CDI recurrence to assess clinical response on each follow-up contact for 60 days after FMT.

If subjects experience diarrhea (3 or more watery stools/day for two consecutive days) and suspect CDI recurrence, they should inform the study team and be recommended to contact their physician to perform a stool test for *C. difficile*. EPDL will test scheduled stool specimens and any unscheduled illness stool submitted up to days 60-70 after treatment for *C. difficile* toxins A/B in weekly batches but this should not delay treatment. If the test is positive, they should be treated by their physician. The Principal Investigator will be available for consultation with the attending physician. A form letter may be faxed or emailed to subject's physician about CDI recurrence.

Subjects requiring a systemic Non- *C. difficile* antibiotic within 60 days following FMT treatment will be excluded from the study for efficacy analysis, but will be followed for safety. Exclusion from efficacy means subjects will no longer provide stool specimens. However, subjects will continue to have phone visits and submit diaries till 180-200 days (the end of the study) for safety assessment (AEs). Subjects requiring a systemic Non- *C. difficile* antibiotic 60 days after FMT treatment will continue to be followed for efficacy and safety.

Subjects will be recommended not to use non-dietary probiotics and bile-acid sequestrants within 60 days after FMT treatment; however, subjects who take probiotics and bile-acid sequestrants within 60 days after treatment will not be excluded and continue

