7.5 Health Outcome Assessment

Information such as mortality from any cause and hospitalizations will be collected through AE assessments. Subjects will report their solicited and unsolicited adverse events to study personnel on follow-up phone visits.

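### Section 9.1.1 exempts CDI recurrence from adverse-event recording through Day 180-200 with a single exit, which conflicts with other safety sections and leaves outpatient recurrence after Day 60 in no planned table

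*Combined protocol and SAP*

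**What the plan says.** Safety and prevention of CDI within 60 days are both primary endpoints (sections 2 and 9.11).

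**Adverse events.** Section 9.1.1 sets the recording window: "All adverse events (AEs) that occur within 180-200 days after treatment will be recorded as indicated above". It then makes one exemption: "Recurrence of CDI is not to be recorded as an adverse event unless hospitalization ≥ 24 hours is required for management". If that condition is met, the event is recorded as an SAE.

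**Seriousness.** Section 9.1.3 begins "Any adverse event or suspected adverse reaction is considered serious if in" and goes on to list outcomes as the investigators judge them. Besides hospitalization of at least 24 hours, these include death, "Life-threatening adverse event", incapacity, and "Important medical events that jeopardize the patient, such as allergic bronchospasm requiring intensive treatment".

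**Other safety text.** Section 7.5 says: "Information such as mortality from any cause and hospitalizations will be collected through AE assessments". Section 9.5 treats symptoms that are new or worse after treatment as an AE.

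**Efficacy.** Section 6 defines treatment failure by diarrhea, a positive toxin test and anti-*C. difficile* antibiotics, within 60 days. Section 7.3 plans an "evaluation of CDI recurrence to assess clinical response on each follow-up contact for 60 days after FMT". Section 7.1, however, describes "180-200 days of follow up for treatment effect and safety".

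**The concern.** Leaving the efficacy outcome out of AE recording is a common and defensible choice, on two conditions: the event is counted somewhere else, and serious cases are still treated as serious. The exemption in 9.1.1 does not secure either condition for the full follow-up.

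On seriousness, it recognizes one criterion out of the list in 9.1.3. IRB reporting (9.1.3), the safety tables and the SAE narratives (10.2.5) all work from recorded AEs and SAEs, so an event that is never an AE does not enter them.

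On counting, efficacy stops at Day 60 and the exemption does not. The trial compares doses, and the presence or absence of bowel preparation and Imodium. If outpatient relapse after Day 60 is not tabulated, the report cannot say whether a group with fewer 60-day failures kept that advantage or only had its recurrences later.

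**Working it through.** The point concerns definitions and time windows. The plan states no figure for it, so there is none to reproduce.

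**Step 1: can a serious recurrence without a 24-hour admission become an SAE?**

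- 9.1.1: a CDI recurrence is not an AE unless a hospital stay of at least 24 hours is needed.
- 9.1.1 also asks the investigator to name the disease rather than its separate symptoms where possible. Followed here, that turns the symptoms into CDI recurrence, which is exempt.
- 9.1.3 applies its criteria to AEs and suspected adverse reactions, and 9.1.2 defines the latter as a kind of AE. An exempt event therefore has no way in.
- 9.5 points the other way, because new or worse symptoms are an AE. Nothing says which section prevails.
- Death: 9.1.1 does not name it as an exit, but 7.5 collects all-cause mortality through AE assessments. This is a conflict of wording.
- Prolonged hospitalization would usually meet the 24-hour condition.

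What remains is a life-threatening, incapacitating or medically important recurrence without a 24-hour stay.

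**Step 2: where is an outpatient recurrence after Day 60 counted?**

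| Element | Ends at | Section |
|---|---|---|
| Treatment failure definition | Day 60 | 6 |
| Primary efficacy endpoint | Day 60 | 2, 9.11 |
| Assessment of recurrence | Day 60 | 7.3, 8.1 |
| Solicited symptoms | Day 60 | 7.2, 8.5 |
| Toxin testing by the study laboratory | Day 60-70 (Day 60 in 9.12) | 7.4, 9.12 |
| AE recording | Day 180-200 | 9.1.1 |
| CDI exemption from AE recording | no limit stated | 9.1.1 |

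The only secondary endpoint is microbiota diversity, and 10.2.5 tabulates AEs and SAEs only. An outpatient recurrence after Day 60 therefore enters no planned table. Days 60-70 are ambiguous, because stools are still toxin-tested while the failure definition has ended.

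**Step 3: length of the uncovered period.** Share = (end of follow-up − end of efficacy window) / end of follow-up.

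- Window to Day 60: (180 − 60)/180 = 120/180 = 67%; (200 − 60)/200 = 140/200 = 70%.
- Window to Day 70: (180 − 70)/180 = 110/180 = 61%; (200 − 70)/200 = 130/200 = 65%.

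**Step 4: possible number of events (illustration only).** Inputs from 10.2.2 are 90 per group and assumed efficacies of 70%, 80%, 88% and 80%. All 360 are taken as treated and followed.

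- Expected failures by Day 60: 90 × (0.30 + 0.20 + 0.12 + 0.20) = 90 × 0.82 = 73.8.
- Free of failure at Day 60: 360 − 73.8 = 286.2.

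The documents give no rate of late recurrence. With assumed rates of outpatient recurrence after Day 60:

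| Assumed rate | Events = 286.2 × rate | About |
|---|---|---|
| 1% | 2.9 | 3 |
| 3% | 8.6 | 9 |
| 5% | 14.3 | 14 |
| 10% | 28.6 | 29 |

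**The case against.** Much can be said for the plan.

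- **Serious events have other routes.** Section 7.5 collects deaths and hospitalizations. Section 9.5 makes new or worse symptoms an AE, and 9.7 tells an investigator in doubt to record the finding. Table 2 grades diarrhea with shock and colitis with perforation or toxic megacolon as life-threatening. A reader might infer from 9.1.1 that fatal recurrences go unrecorded, or that every criterion except hospitalization is bypassed. The documents do not support that: deaths reach the data through 7.5, prolonged stays usually meet the 24-hour rule, and congenital anomaly is irrelevant to a recurrence. These routes narrow the gap but do not close it. They compete with an explicit instruction in 9.1.1, and two investigators could record the same event differently.

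- **Late recurrence leaves traces.** The Day 90 and Day 180 calls ask about new illness symptoms and medication changes, and bowel-movement diaries continue to Day 180. A reader might infer that late recurrence vanishes from the data altogether, and that would be wrong. But these traces do not record a toxin result, and no analysis uses them.

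- **Durability is not an objective.** Sections 2 and 9.11 limit prevention to 60 days, and section 3 describes the long follow-up as being for safety. This stands as a defence of the 60-day endpoint, which is not challenged here. It does not explain why the exemption continues once efficacy no longer counts the event.

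- **A comparison of late recurrences alone would mislead.** Failures are not followed further for clinical parameters, and retreated subjects leave the study (section 6). Those still at risk after Day 60 are a subset selected after randomization. This is correct and shapes the fix.

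**Conclusion.** The point holds in two parts.

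1. As worded, 9.1.1 keeps a life-threatening, incapacitating or medically important recurrence without a 24-hour admission from being an AE, and so from 9.1.3. Sections 7.5, 9.1.1, 9.1.3 and 9.5 must be reconciled. The documents give no basis for a frequency, and such events may be few.

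2. An outpatient recurrence after Day 60 is in neither the efficacy endpoint nor the AE tables. The period is 67-70% of follow-up days, or 61-65% if Days 60-70 are credited. A reader might take this as the share of recurrences missed. It is calendar time only, and the documents say nothing about when recurrences fall. The illustrative 3 to 29 events rest on assumed rates of 1% to 10%, on the plan's own assumed efficacies and on complete follow-up.

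The 60-day primary efficacy result is unaffected. The change is worth making because safety is a primary endpoint and because information not asked for during follow-up is hard to recover afterwards.

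**What to change.** 1. **Section 9.1.1:** let any seriousness criterion in 9.1.3, including death, end the exemption, in place of the 24-hour hospitalization alone. Align 7.5 and 9.5 with it, and state how Days 60-70 are treated.

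2. **Sections 7.3, 8.1 and 8.5:** ask the recurrence question (diarrhea, local toxin result, anti-CDI antibiotic, date) at the existing Day 90 and Day 180 calls.

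3. **Section 10.2:** report descriptively, by randomized group, cumulative CDI recurrence through Day 180-200 in all treated subjects, with failures by Day 60 counted as events. Add a listing of recurrences after Day 60. Counting early failures as events keeps the randomized groups whole even though failures are not followed further. Subjects removed from efficacy for a systemic antibiotic still have their calls under 4.8, so the question reaches them.

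4. Keep the 60-day primary endpoint unchanged.

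The cost is an amendment to the wording, a few more items at two calls that already take place, and one descriptive table with a listing. No visit or study test is added. The limitation is that late recurrences would be confirmed only by local tests, because study-laboratory toxin testing ends at Day 60-70.

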 - On Day -1, all subjects must follow a clear liquid diet the entire day. In the evening around 6:00pm, subjects (treatment groups 1-3) must take bowel preparation i.e. 1 bottle (10 oz.) of magnesium citrate or patients with impaired kidney function take 250mL of GoLytely. GoLytely will be prescribed by the investigator or nurse practitioner. If bowel prep is missed, subject can still proceed with FMT (noted as protocol deviation).

- On Day 1, subjects (treatment groups 1-3) will take 4mg (2 capsules) of loperamide (Imodium) the morning of treatment (if Imodium is missed, can be taken within 12 hours after FMT treatment).
- On Day 1, subjects take first dose of oral capsules of PRIM-DJ2727 and recommended to continue their clear liquid diet for 1 hour after dosing.
- Stool samples will be collected by the subject before FMT and at follow up days 1, 7, 14, 30, 60, 90 and any unscheduled visit up to 60-70 days after FMT treatment and brought to the EPDL within 6 hours of collection if possible or as quickly as possible (excluding weekends and holidays). Subject can collect pre-treatment stool on any day after enrollment and before bowel prep on Day -1, and can bring stool sample on treatment day 1 clinic visit. If a subject is unable to bring the sample to the EPDL (e.g. out of town), it may be shipped by Federal Express as expeditiously as possible. A FedEx shipping label, ice pack, Styrofoam container with shipping box and instructions will be provided to subjects to ship stool sample if they are not able to hand deliver to the EPDL. The EPDL will be closed on weekends and holidays. If the follow-up day falls on Friday, Saturday or Sunday, subjects can ship the sample on Thursday or the following Monday.
- Subjects should inform the study team if they experience diarrhea (passage of ≥ 3 watery stools per 24-hour period for two consecutive days) suspecting CDI recurrence and contact their physician to perform a stool test for *C. difficile*. The EPDL will test scheduled stool specimens and any unscheduled illness stool submitted up to 60-70 days after treatment for *C. difficile* toxins A/B in weekly batches but this should not delay treatment. If the test is positive, they should be treated by their physician. The Principal Investigator will be available for consultation with the attending physician. A form letter may be faxed or emailed to subject's physician about CDI recurrence.

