13. CONTACTS ABOUT STUDY

For study details, the study coordinators at Kelsey Research Foundation [REDACTED] |

For product related issues - [name] [REDACTED]

For subjects at Kelsey-Seybold Clinic - [name] [REDACTED]

For University of Texas/Memorial Hermann Hospital - [name] [REDACTED] The
University of Texas Health Science Center Committee for the Protection of Human Subjects
[REDACTED].

Kelsey Seybold Clinic Review Committee at [REDACTED]

TABLE 1: STUDY SCHEDULE:

Assessment and Procedures	Enrollment (day -14 to -1)	Treatment Days		Follow Up and Safety Assessment Period via Telephone							Un scheduled Visit	Early Termination Visit
		Day 1	Day 2	Day 1 (+3)	Day 7 (+3)	Day 14 (+3)	Day 30 (+10)	Day 60 (+10)	Day 90 (+10)	Day 180 (+20)		
	Clinic	Clinic	Phone	Phone	Phone	Phone	Phone	Phone	Phone	Phone	Phone	Phone
Informed Consent	X											
Inclusion/Exclusion Criteria	X											
Demographics	X											
Medical/CDI History	X											
Concomitant medications	X			X	X	X	X	X	X	X		
Randomization at University of Texas School of Public Health	X											
Pre-treatment preparation reminder (day -4 to -1) ¹	X											
Urine Pregnancy Test ²		X										
Confirmation of bowel prep and Imodium (groups 1-3) ³		X										
Vital signs ⁴ and Weight ⁵		X										
Stool Collection	X ⁶			X	X	X	X	X	X	X	X	
Study Drug Dose		X	X									
Diaries Distribution	X	X										
Diaries Receipt ⁷		X			X	X	X	X	X	X		X
AE Assessment/Monitoring for Safety		X	X	X	X	X	X	X	X	X	X	X

¹ Reminder can be via email or phone.

² Perform urine pregnancy test only on female subjects' of childbearing potential

³ If bowel prep is missed, subject can still proceed with FMT (noted as protocol deviation).

⁴ Vital signs before treatment, observe, and repeat vitals after at least 60 minutes

⁵ Weight measured before treatment only. Subjects will measure weight at home each Sunday morning before eating and record on diaries if they have a scale or balance.

⁶ Subject can collect stool any day after enrollment and before bowel prep on Day -1, and can bring stool sample on treatment day 1 clinic visit

⁷ Diaries can be submitted with stool samples or emailed, faxed or mailed (original can be provided later)

TABLE 2: SEVERITY GRADING

Parameter	Grade 1: Mild	Grade 2: Moderate	Grade 3: Severe	Grade 4: Potentially Life-threatening

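### Baseline weight follows bowel prep in groups 1-3 but not in group 4, so the >5% weight-change rule could show a spurious difference between groups 3 and 4

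*Combined protocol and SAP*

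**What the plan says.** Weight gain is one of three adverse events of special interest in section 9.1.5. For baseline, "subjects will be weighed on treatment day 1 clinic visit prior to administration of FMT treatment". There is no later clinic weight; footnote 5 to Table 1 reads "Weight measured before treatment only". After treatment, "subjects will be recommended to measure weight at home each Sunday morning before eating", provided they own a scale. The rule is that "subject-reported weekly weight data from diaries will be assessed for AE (>5% change from baseline weight", applied at the day 60 and day 180 phone visits. It states no direction.

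Section 8.1 sets the preparation for Day -1. The diet is common to all: "On Day -1, all subjects must follow a clear liquid diet the entire day". The prep is not: "In the evening around 6:00pm, subjects (treatment groups 1-3) must take bowel preparation". It consists of "1 bottle (10 oz.) of magnesium citrate or patients with impaired kidney function take 250mL of GoLytely". Group 4 receives the same product dose as group 3 without prep or Imodium (section 5.2). A subject in groups 1-3 who misses prep is still treated, and the miss is recorded as a deviation.

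Section 10.2.3 makes the safety and efficacy comparison of groups 3 and 4 one of two primary analyses. Section 10.2.1 defines baseline for all analyses as the date of transplantation. No baseline weight before prep, no baseline on the home scale and no adjustment is planned.

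**The concern.** Prep, with Imodium, is the factor that separates group 3 from group 4, and it comes before the measurement that serves as baseline. A lower baseline in group 3 makes an unchanged later weight look like a gain and hides part of any real loss. The 5% margin is there to absorb ordinary fluctuation; a prep effect would use up part of it in one group only.

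The protocol guards against prep elsewhere. Section 7.2 places the baseline stool sample before prep and ends the pre-treatment symptom diary before prep. Section 9.5 expects mild to moderate diarrhea from prep in groups 1-3 and keeps it out of the adverse event record. Baseline weight has no such protection. At stake is how one named event of special interest reads in the comparison of group 3 with group 4.

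**Working it through.** The documents state no rate, power or error figure for weight change, so there is nothing of the plan's own to reproduce. The check is an illustration.

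**From the documents:** a 5% threshold; prep before the baseline weight in group 3 and none in group 4; 90 subjects per group (section 10.2.2).

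**Assumed, because the documents are silent:** true change c from unprepped weight is normal with mean 1% and SD 4%; prep lowers the group 3 baseline by a further s = 0%, 0.5% or 1% of body weight, beyond whatever the shared diet does. At 70 kg, 0.5% is 0.35 kg, 1% is 0.7 kg and the threshold is 3.5 kg.

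**Formulas.** If the unprepped weight is W, the group 3 baseline is W(1 - s), so measured change = (1 + c)/(1 - s) - 1. A gain is flagged when c > 1.05(1 - s) - 1, and a loss when c < 0.95(1 - s) - 1. Group 4 is the case s = 0.

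- s = 0: cut-offs +5% and -5%; z = (5 - 1)/4 = 1.00 and (-5 - 1)/4 = -1.50.
- s = 0.5%: cut-offs +4.475% and -5.475%; z = 0.869 and -1.619.
- s = 1%: cut-offs +3.95% and -5.95%; z = 0.738 and -1.738.

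| Extra loss from prep | Gain >5% | Loss >5% | Either |
|---|---|---|---|
| 0% (group 4) | 15.9% | 6.7% | 22.5% |
| 0.5% (group 3) | 19.2% | 5.3% | 24.5% |
| 1% (group 3) | 23.0% | 4.1% | 27.2% |

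If all 90 subjects per group gave weights, the spurious excess of gains in group 3 would be 0.033 x 90 = 3.0 subjects at s = 0.5% and 0.071 x 90 = 6.4 at s = 1%. The excess in the undirected count would be 0.020 x 90 = 1.8 and 0.047 x 90 = 4.2.

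**Sensitivity.** With mean 0%, SD 4% and s = 1%, gains go from 10.6% to 16.2%, but the undirected count only from 21.1% to 23.0%. Over means of 0-3% and SDs of 2-5%, the excess of gains is about 1-7 points at s = 0.5% and 2-16 points at s = 1%.

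**Scale switch.** A home-scale offset of -1% or +1% moves the group 4 gain rate to 10.6% or 22.7%. With s = 0 group 3 has exactly the same rates, so the offset alone creates no group difference.

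**After the fix.** If both groups are weighed in the same condition, s = 0 for both, and the expected difference from this source is zero in every scenario.

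**The case against.** The strongest reply is that the asymmetry may be too small to matter. All four groups are on clear liquids on Day -1, so only the additional loss from prep counts. The prep is small in volume and is itself swallowed as fluid. Missed preps dilute the contrast further. All of this stands and points to the low end of the range, possibly close to zero. A reader might infer a shift of one or two kilograms, with gain flags rising to match; nothing in the documents supports a figure of that size.

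The consequences are also limited. Section 10.2.5 only tabulates adverse events, and no test of weight is planned. The rule has no direction, so extra gains and missing losses partly cancel in a total. The text has weights assessed by study staff, not flagged automatically, and a recalled weight from before the first CDI episode is collected as context. These points limit the harm without removing the asymmetry: the cancelling does not help for gain, which is the named event, and the recalled weight is not part of the >5% rule.

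A reader might also infer that moving from the clinic scale to home scales biases group 3 against group 4. It does not. The switch applies to every group; it adds error and can shift all rates together, but it does not itself separate the two groups.

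**Conclusion.** The concern holds as a possibility of bias, not as a demonstrated one. The documents establish that the baseline weight for the >5% rule is taken after prep in groups 1-3 and without prep in group 4, and that nothing corrects for this in a comparison the plan calls primary. If prep lowers weight at all beyond the shared diet, the direction is fixed: more apparent gains and fewer apparent losses in group 3. Under the stated assumptions the excess of gains is 3.3 points at an extra loss of 0.5% and 7.1 points at 1%, and the undirected count rises by 2.0 and 4.7 points. The extra loss, the mean and the SD are all assumptions.

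The documents do not support extending the point to the dose comparison, since groups 1-3 are all assigned the same prep. This is a minor point, worth acting on because the remedy is cheap and a weight before prep cannot be recovered afterwards.

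**What to change.** Add one line to the pre-treatment diary for a home-scale morning weight before bowel prep, and use it as the baseline for the >5% rule in all groups. Because group 4 has no prep to date it by, define the time for everyone as no later than the morning of Day -1. This removes the prep asymmetry wherever the weight is recorded, and puts baseline and follow-up on the same kind of scale.

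State in section 9.1.5 that:

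- no weight taken after FMT may stand in for a missing baseline, because it could absorb an early treatment effect;
- where the home weight before prep is missing, results against the Day 1 clinic weight are shown separately and labeled as such;
- the clinic weight is otherwise descriptive;
- gain and loss are tabulated separately.

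Section 10.2.1 needs a matching exception to its definition of baseline.

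The cost is one diary line and a few sentences, with no change to treatment or preparation. The downside is that the baseline becomes self-reported. It will be missing for subjects without a scale, who already provide no follow-up weights, and possibly for anyone enrolled as late as Day -1.
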